**Objectives:**

- Primary: to determine the efficacy of quintuple therapy against COVID-19 infection
- Secondary: To assess the safety and tolerability of treatment with quintuple therapy in Subjects with COVID-19 infection

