## 2. Trial Objectives

Primary Study Objective	Study Endpoints
The rate of recovery of mild or moderate COVID-19 in Subjects using Quintuple Therapy	Number of Days Recovery from COVID-19 diagnosis to Recover via RT-PCR
Secondary Objectives	Study Endpoints
Assess the safety of Quintuple Therapy	Assess the symptom response to study therapy as measured by the survey in the EDC
	EKG response, oxygen saturation, and vital signs at baseline, 2 weeks, 1 month, and two months
Assess Tolerability of Quintuple Therapy	Assess Adverse Events and Serious Adverse Events due to Quintuple Therapy

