### **13. Risk/Benefit Assessment**

#### **13.1 Potential Risks**

- Confidentiality Risks: All data (clinical, demographic, etc.) for individual subjects will be provided to ProgenaBiome. Information obtained during the study will not be shared outside the study personnel except in scientific reports or publications in aggregated and deidentified form.

- Risks associated with Hydroxychloroquine
  - Auditory
    - Tinnitus
    - Hearing loss
  - Cardiovascular
    - Cardiomyopathy (can result in fatal cardiac failure)
    - biventricular hypertrophy
    - Prolongation of Q-T Interval
  - Dermatologic
    - Pigmentary changes in skin and mucous membranes
      - Usually reversible upon discontinuation of medication
    - Bleaching of hair
      - Usually reversible upon discontinuation of medication
    - Alopecia
      - Usually reversible upon discontinuation of medication
    - Rash/pruritus
    - AGEP
      - Usually reversible upon discontinuation of medication
    - Outbreak of psoriasis, occasionally associated with fever and hyperleukocytosis
    - Urticaria
    - Angioedema
    - Bullous eruptions including
      - Erythema multiforme
      - Stevens-Johnson syndrome
      - Toxic epidermal necrolysis
    - DRESS syndrome
    - Photosensitivity
    - Exfoliative dermatitis
  - Gastrointestinal
    - Abdominal pain
    - Nausea
    - Diarrhea
    - Vomiting
  - Hematologic
    - Bone marrow suppression
    - Anemia
    - Aplastic anemia
    - Agranulocytosis
    - Leukopenia
    - Thrombocytopenia
  - Hepatic
    - Fulminant hepatic failure
  - Metabolic
    - Anorexia
    - Hypoglycemia
    - Exacerbation or precipitation of porphyria
  - Musculoskeletal
    - Sensorimotor dysfunction
    - Skeletal muscle myopathy or neuromyopathy

- May be reversible by stopping medication but recovery could take months
  - Depression of tendon reflexes
  - Abnormal nerve conduction studies
- Nervous system
  - Headache
  - Dizziness
  - Seizure
  - Vertigo
  - Auditory nerve dysfunction
  - Ataxia
- Optical
  - Blurred vision
    - Dose dependent and reversible upon discontinuation of medication
  - Retinopathy with changes in pigmentation and other visual field defects
    - Subjects with retinal changes may be asymptomatic initially, or may have scotomatous vision with paracentral, pericentral ring types, temporal scotomas, and abnormal color vision.

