## 15. Statistical analysis

The treated patients in this study will be compared to the placebo group. Measurements will include PCR test results, presence or absence of symptoms, and symptom severity. PCR results will be compared between the groups as positive or negative

In this study, the meaningful threshold will be calculated as mean change in clinical symptoms as recorded in the diary, from Day 1 through week 12. Each category in the diary will be assigned a number, 0 for None, 1 for Mild, 2 for Moderate and 3 for severe. Each category will be analyzed independently and they will be analyzed as a group. Ultimately, efficacy will be determined based upon reduction and/or progression of symptomatic days, reduction of symptom severity, as well as analysis of the subject's RT-PCR testing per protocol. These data will be compared to an existing database of de-identified Subject data.

The change of these measurements from the end to the baseline (post-pre) will be used as the primary outcome, for example,  $\mu_e = \mu_{e1} - \mu_{e0}$ , where  $\mu_{e1}$  and  $\mu_{e0}$  are the outcome of Subjects from the treatment group at the end and at baseline, respectively.

Categorical variables will be summarized by presenting the number (n) and percent (%) of subjects in each category. All Statistical tests for the analysis will be performed using the  $p < 0.05$  level of significance. All confidence intervals will be one-sided

Sample size was calculated as follows:

$$n = \frac{\log \beta}{\log \rho}$$

Where  $\beta = \text{the probability of a Type II error}$

$\rho = \text{the proportion of the population NOT affected}$

The proportion of the population affected by COVID-19 is 0.005 percent, thus 0.995 percent aren't affected

The probability of a type II error is 0.05

Thus:

$$n = \frac{\log 0.050}{\log 0.995}$$

$$n = 597.647$$

A sample size of 600 will be used

Additional details can be found in the Statistical Analysis Plan that will be developed prior to database lock.

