## 16. Adverse Event Analysis

All adverse events and serious adverse events will be analyzed to determine likelihood of association with treatment. Likely and known Treatment Emergent Events will be tabulated and summarized by presenting the incidence number (number and percentage of subjects) in each treatment group. No inferential analyses will be performed on safety parameters.

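### Safety is the secondary objective of a placebo-controlled trial, but Section 16 leaves every between-arm safety difference without a confidence interval

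*Combined protocol and SAP*

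**What the plan says.** The synopsis (Objectives) gives the secondary objective as "To assess the safety and tolerability of treatment with quintuple therapy in Subjects with COVID-19 infection". Section 2 (Trial Objectives) lists the endpoints beneath it. They include "EKG response, oxygen saturation, and vital signs at baseline, 2 weeks, 1 month, and two months" and "Assess Adverse Events and Serious Adverse Events due to Quintuple Therapy". Section 13.1 names "Prolongation of Q-T Interval" among the hydroxychloroquine risks, and Appendix 4 makes QT findings a reason for stopping in a subject, so QT is a safety measure the protocol itself treats as important.

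Section 16 is the whole of the safety analysis: "Likely and known Treatment Emergent Events will be tabulated and summarized by presenting the incidence number", as number and percentage of subjects in each treatment group, followed by "No inferential analyses will be performed on safety parameters". Section 15 adds a general rule, "All confidence intervals will be one-sided", without giving a direction and without assigning any interval to safety. Section 15 also says that a Statistical Analysis Plan with further detail will be written before database lock.

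**The concern.** The two arms take the same vitamins and zinc and differ only in hydroxychloroquine and azithromycin versus matching placebos. The natural safety quantity is therefore the difference between arms. Nowhere do the documents define such a difference or its uncertainty.

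Avoiding a long list of p-values on adverse events is sound. A rule against all inferential analyses goes further: in the ordinary meaning of the words it also excludes a confidence interval. What remains is two columns of percentages. When events are few, such columns are easily read as showing that the regimens are equally safe, although the same data may be compatible with an excess that matters. The trial would then report on its secondary objective without saying how large an excess of harm its data rule out.

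**Working it through.** **1. The plan's own figure.** Section 15 takes n = log β / log ρ, stating "The probability of a type II error is 0.05" and computing with ρ = 0.995:

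log(0.05) / log(0.995) = 597.647, rounded up to 600. This reproduces.

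The formula gives the number of subjects needed to see at least one event of probability 0.005 with 95% probability. It is a single-group calculation, so the sample size tells us nothing about the precision of a between-arm safety comparison. That has to be worked out separately.

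**2. Inputs.**
- Total: 600 (Section 15; the synopsis aims for at least 600 completers).
- Allocation: two arms, ratio not stated. I assume 300/300 and show 400/200 as a range.
- Event rates: the documents give none, so the counts below are illustrative.

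**3. Interval for a risk difference.** I use the Newcombe interval, built from the Wilson limits (l, u) of each arm, with z = 1.96 and d = p1 - p2 (treatment minus placebo):

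- lower = d - √[(p1 - l1)² + (u2 - p2)²]
- upper = d + √[(u1 - p1)² + (p2 - l2)²]

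For no events in n subjects, the Wilson limits are 0 and z²/(n + z²). With n = 300 the upper limit is 3.84/303.84 = 1.26%. With 0 v 0 events the interval is therefore -1.26 to +1.26 points. For 400/200 the limits are 3.84/403.84 = 0.95% and 3.84/203.84 = 1.88%, giving -1.88 to +0.95 points.

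Equal observed rates, two-sided 95% interval in percentage points:

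| Rate in both arms | 300/300 | 400/200 |
|---|---|---|
| 0% | -1.26 to +1.26 | -1.88 to +0.95 |
| 1% | -2.01 to +2.01 | -2.64 to +1.70 |
| 5% | -3.65 to +3.65 | -4.32 to +3.44 |

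Unequal counts at 300/300:

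| Events, treatment v placebo | Difference | 95% interval |
|---|---|---|
| 3 v 0 | +1.0 | -0.4 to +2.9 |
| 15 v 6 | +3.0 | -0.01 to +6.3 |
| 60 v 30 | +10.0 | +4.3 to +15.7 |

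Within one arm, the exact two-sided 95% upper limit for 0 of 300 is 1 - 0.025^(1/300) = 1.22%.

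So an observed rate of 1% in both arms leaves room for a doubling or tripling of risk (an excess of up to 2.0 points on a base of 1%).

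**4. What could be recovered from the planned output.**
- *Events tabulated by arm under Section 16:* yes, from the counts and arm sizes, as above.
- *Any AE or any SAE:* not from the planned tables. Only a subset of events is tabulated by arm, and rows cannot be added because one subject may have several events.
- *EKG/QT, oxygen saturation, vital signs:* no. Sections 15 and 16 plan no mean, standard deviation or category count for them, so neither a difference nor an interval can be derived.

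**5. The one-sided rule.** If safety intervals were added under Section 15 as it stands, each would be one-sided in an unstated direction. At 300/300 and 0 v 0 events, a one-sided 95% upper bound is +0.89 points. A bound placed on the other side would say nothing about excess harm. An explicit exemption is needed.

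**The case against.** The case for leaving the section alone has real substance.

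- *Descriptive safety reporting is a legitimate choice.* The objective is worded as an assessment, and the documents set no safety hypothesis, margin or target rate. A reader might infer that Section 16 contradicts the objective or makes it unanswerable. The documents do not support that. Nor would tests help much: with 300 per arm and two-sided 5% significance, power is 17% for 1% v 2% and 42% for 1% v 3%. This stands against adding tests. It does not tell against intervals, because low power is a reason to show the uncertainty.
- *Counts are published.* A reader might infer that an absence of difference can never be distinguished from too few events. That is too strong. For every tabulated event the interval follows from the counts, so the information is there but not presented. The reply fails for QT, oxygen saturation and vital signs, and for events outside the tabulated subset.
- *Point estimates are not barred.* A reader might take Section 16 to forbid even a risk difference or a mean QT difference. Those are descriptive, and the sentence does not exclude them. They are simply not planned. Only the interval falls under the prohibition.
- *A later SAP is promised.* It could add summaries and point differences. It could not add confidence intervals without going against the protocol's flat statement, so the protocol sentence has to change first.

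**Conclusion.** The point holds as a cheap improvement to reporting. No between-arm safety difference will be presented with a confidence interval, and for QT/EKG, oxygen saturation and vital signs a reader could not supply one. The consequence is largest for uncommon events: 0 v 0 leaves about ±1.3 points, and equal 1% rates leave about ±2.0 points.

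These figures rest on 600 subjects split 1:1 and on illustrative event counts. The 400/200 range in the working shows that unequal allocation changes the limits but not the conclusion. They show what intervals would add. They do not show that the trial will mislead.

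**What to change.** Replace the last sentence of Section 16 with wording such as:

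> Safety data will not be subjected to hypothesis tests. Between-arm differences with two-sided 95% confidence intervals will be reported for any AE, any SAE, study-drug discontinuation for QT, gastrointestinal AEs, and mean and maximum QT change from baseline. These intervals are descriptive, are not adjusted for multiplicity, and are exempt from the one-sided rule in Section 15.

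Cost: no new data or subjects, since AEs and SAEs are already collected and home EKG is already transmitted daily through Day 10. It does need a few additional tables, because any-AE, any-SAE and QT summaries are not currently planned. The intervals are unadjusted, so each table must carry the descriptive label to keep a single interval that excludes zero from being read as a test result. The change touches no dose, stopping rule or other aspect of clinical management.

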## 17. Regulatory Compliance

This study will be conducted in accordance with protocol and applicable requirements outlined in FDA Code of Federal Regulations (CFR) Title 21 and the International Conference on Harmonization (ICH) E6 Good Clinical Practice.

### 17.1 Principal Investigator

The Principal Investigator, together with any designated Sub-Investigators, has the overall responsibility for the

conduct and compliance of this clinical trial according to this protocol and Good Clinical Practice (GCP).

### **17.2 Record Retention**

Per FDA and ICH GCP requirements, ProgenaBiome requires that all study related documentation be retained up to 2 years after the last sample has been processed or as mandated by the institution, whichever is longer.

## **18. Financial Obligations and Compensation**

### **18.1 Financial Obligations of the Subjects**

The subjects will not incur financial obligations by participation in this study

## 20. Appendices

### 20.1 Appendix 1: MoMe Kardia II EKG Specifications and Instructions

[figure not shown]
Specification	MoMe® Kardia Device
Battery Life	Provides 24 hours of function before recharging
Operating Temperature	5°C to 40°C
Storage Temperature (power off)	-25°C to 70°C
Operating Humidity	15% to 93% non-condensing
Storage Humidity	15% to 93% non-condensing
Operating Pressure	700 hPa to 1060 hPa
ECG	
Sampling Rate	200 Hz
Digital Resolution	5uV
Input Dynamic Range	+/- 10 mV
Input Offset Dynamic Range	+/- 300 mV
Input Impedance	> 3 MOhm
Peak current injection	24 nA (Lead off circuit) DC
RMS current injection	29 microA
Data Storage Capacity	Minimum 30 days
Dimensions	108 mm x 67 mm x 17 mm max
Weight	80 +/- 5 g
Communication Means	HSPA+, UMTS, GPRS, EDGE 800/850, AWS1700, 1900
Ingress Protection Rating	IPX0
Display	Type: LED Matrix, Size: 24 X 7
Memory	Internal microSD card up to 32 GB, Not user accessible
Battery	Li-Ion 1900mAh battery pack Min 24 hour battery life

## Benefits

-  3-in-1 outpatient mobile cardiac monitor:  
Holter, MCT, and event monitor
-  Lightweight, one piece, sleek form factor
-  Eliminates intermediaries in patient enrollments and IDTF data delays, which may provide faster time to diagnosis
-  On-demand, full disclosure wireless device with automated analysis in the cloud
-  Practices gain full control over diagnostic workflow, including billing

Distributed by  
  
 excellence for life

LEADSET 2

ATTACHMENTS

[https://youtu.be/L0oKWp\\_PHbl](https://youtu.be/L0oKWp_PHbl)

RECORD

Press and hold the Record Button for 3 seconds to record

VOLUME

BATTERY

[figure not shown]

**BATT LOW**

Replace the battery with a fully charged one when the BATT LOW notification is displayed

### Patient Instructions

- This is not a life-saving device and is only monitoring your heart rhythm
- DO NOT Get MoMe Kardia Wet – remove before bathing
- Change Battery every 24 Hours and replace used battery on charger
- Contact your physician's office directly with questions/problems

- WARNINGS**
- MoMe® Kardia is not intended for use as an emergency medical response system. Call 911 if you feel you are having a medical emergency.
  - The MoMe® Kardia Device is not defibrillation-proof. Remove MoMe® Kardia Device and disconnect patient leads before external defibrillation.
  - Do not service or repair any components of the MoMe® Kardia system. Removal of or tampering with any component may alter device performance and cause device malfunction or failure.
  - The MoMe® Kardia contains a cellphone. If you have an implantable device, follow your implantable device manufacturer's recommendations for use with a cellphone.

- CAUTIONS**
- Electrodes may cause skin irritation. Follow your physician's instructions on what to do if skin irritation occurs.
  - Use only with the supplied battery packs, charging dock, and wall adapter
  - MoMe® Kardia is not waterproof:
    - Do not get device wet. Never bathe, shower, or swim while wearing the MoMe® Kardia Device (while bathing or swimming, store MoMe® Kardia equipment in a safe, dry location)
    - Protect all MoMe® Kardia parts from water, liquids or moisture which will damage equipment and affect system operation;
    - Do not immerse any part of the MoMe® Kardia system in water or fluids. Do not spray device with cleaners or other liquids;
  - Do not drop or subject MoMe® Kardia parts to extreme physical shock.
  - Keep the system out of reach of children and pets.
  - The MoMe® Kardia provided for use in the U.S. will not transmit recorded data if you travel outside of the U.S.

**MoMe® Kardia  
Patient Quick Reference Guide**

10609a

Your physician prescribed you a MoMe® Kardia device. It is important you wear the device according to your doctor's instructions.

**LEADSET**

**ATTACHMENTS**

line up battery pack  
insert tabs  
push down and in to slide lock over

[figure not shown]
Slide device into Belt Clip to lock into position  
Attach the leadset as shown above.

**VOLUME**

**RECORD**

**NOTIFICATIONS**

Replace the battery with a fully charged one when the BATT LOW notification is displayed

- WARNINGS**
- MoMe® Kardia is not intended for use as an emergency medical response system. Call 911 if you feel you are having a medical emergency.
  - The MoMe® Kardia Device is not defibrillation-proof. Remove MoMe® Kardia Device and disconnect patient leads before external defibrillation.
  - Do not service or repair any components of the MoMe® Kardia system. Removal of or tampering with any component may alter device performance and cause device malfunction or failure.
  - The MoMe® Kardia contains a cellphone. If you have an implantable device, follow your implantable device manufacturer's recommendations for use with a cellphone.

- CAUTIONS**
- Electrodes may cause skin irritation. Follow your physician's instructions on what to do if skin irritation occurs.
  - Use only with the supplied battery packs, charging dock, and wall adapter
  - MoMe® Kardia is not waterproof:
    - Do not get device wet. Never bathe, shower, or swim while wearing the MoMe® Kardia Device (while bathing or swimming, store MoMe® Kardia equipment in a safe, dry location)
    - Protect all MoMe® Kardia parts from water, liquids or moisture which will damage equipment and affect system operation;
    - Do not immerse any part of the MoMe® Kardia system in water or fluids. Do not spray device with cleaners or other liquids;
  - Do not drop or subject MoMe® Kardia parts to extreme physical shock.
  - Keep the system out of reach of children and pets.
  - The MoMe® Kardia provided for use in the U.S. will not transmit recorded data if you travel outside of the U.S.

---

## MoMe® Kardia Patient Quick Reference Guide

---

## Specification Sheet

### Product Highlights

MoMe® Kardia is an advanced 3-in-1 outpatient mobile cardiac monitoring solution that allows physicians to dynamically switch between Holter, MCT, and event monitoring modes for up to 30 days of continuous monitoring.

MoMe® Kardia is the first and only FDA cleared remote cardiac monitoring platform that provides near real-time full disclosure data.

abarelix	buprenorphine	daunorubicin liposomal	formoterol
abiraterone	cabazitaxel	degarelix	foscarnet
acetohehexamide	cabergoline	desipramine	galantamine
adalimumab	cabozantinib	deutetrabenazine	gatifloxacin
adenosine	calaspargase pegol	dicloxacillin	gemifloxacin
ado-trastuzumab	calcium carbonate	dicumarol	gilteritinib
emtansine	cannabidiol	digitoxin	glasdegib
afatinib	carbenicillin	digoxin	glimepiride
albuterol	carboplatin	dihydroergotamine	glipizide
alfuzosin	carfilzomib	dinutuximab	glyburide
afatinib	casanthranol	disopyramide	glycerin
aliskiren	cascara sagrada	disulfiram	gold sodium thiomalate
aluminum carbonate	castor oil	docetaxel	golimumab
aluminum hydroxide	ceritinib	dofetilide	goserelin
amifampridine	cerivastatin	dolasetron	granisetron
amiodarone	certolizumab	donepezil	grepafloxacin
amisulpride	cevimeline	doxepin	halofantrine
amitriptyline	chloramphenicol	doxepin topical	haloperidol
amoxicillin	chloroquine	doxorubicin	halothane
amoxapine	chlorpromazine	liposomal	histrelin
ampicillin	chlorpropamide	dronedarone	hydralazine
anagrelide	cholera vaccine, live	droperidol	hydroxyzine
anisindione	cimetidine	duloxetine	ibutilide
apalutamide	ciprofloxacin	edoxaban	idarubicin
apomorphine	cisapride	efavirenz	idelalisib
arformoterol	cisplatin	elotuzumab	iloperidone
aripiprazole	citalopram	encorafenib	imipramine
arsenic trioxide	clarithromycin	enfortumab vedotin	indacaterol
asenapine	clofarabine	entrectinib	indium oxyquinoline in- 111
asparaginase erwinia	clofazimine	enzalutamide	infiximab
chrysanthemi	clomipramine	epirubicin	inotuzumab ozogamicin
asparaginase escherichia coli	cloxacillin	eribulin	interferon alfa-2a
astemizole	clozapine	ergonovine	interferon alfa-2b
atomoxetine	codeine	ergotamine	interferon alfa-n1
atorvastatin	colchicine	erythromycin	interferon beta-1a
attapulgite	crizotinib	escitalopram	interferon beta-1b
auranofin	cyclosporine	estradiol	interferon alfacon-1
aurothioglucose	dapsone	etanercept	iodoquinol
bacampicillin	darifenacin	ethambutol	ipilimumab
balsalazide	dasatinib	ethinyl estradiol	isoetharine
bcg	daunorubicin	ethionamide	isoniazid
bedaquiline	daunorubicin liposomal	etoposide	isoproterenol
benznidazole	deferiprone	etravirine	ivabradine
bepidil	degarelix	ezogabine	ivosidenib
betrixaban	desipramine	famotidine	ixabepilone
bicalutamide	deutetrabenazine	fesoterodine	ixazomib
binimetinib	didanosine	fingolimod	kaolin
bisacodyl	digoxin	flecainide	ketoconazole
bitolterol	dihydroxyaluminum	fluconazole	lactitol
black cohosh	sodium carbonate	fludarabine	lactulose
bortezomib	dabigatran	fluoxetine	lanthanum carbonate
bosutinib	daclizumab	fluphenazine	lapatinib
brentuximab	dasatinib	flutamide	lefamulin
	daunorubicin	fluvastatin	

leflunomide	norfloxacin	propofol	thioridazine
lenvatinib	nortriptyline	propoxyphene	theophylline
leuprolide	ofloxacin	protriptyline	ticarcillin
levabuterol	olanzapine	quetiapine	timolol ophthalmic
levodopa	olodaterol	quinapril	tinidazole
levofloxacin	ondansetron	quinidine	tizanidine
levomethadyl acetate	osilodrostat	quinine	tocilizumab
linezolid	osimertinib	rabies vaccine, human	tolazamide
lithium	oxacillin	diploid cell	tolbutamide
lofedidine	oxaliplatin	rabies vaccine, purified	tolterodine
lomefloxacin	oxtriphylline	chick embryo cell	toremifene
lomitapide	paclitaxelpaclitaxel	ranolazine	trabectedin
loperamide	protein-bound	red yeast rice	tramadol
lovastatin	paliperidone	repaglinide	trazodone
lusutrombopag	palonosetron	ribociclib	triclabendazole
macimorelin	panobinostat	rilpivirine	trifluoperazine
magaldrate	papaverine	riociguat	triflupromazine
magnesium carbonate	pasireotide	risperidone	trimeprazine
magnesium citrate	pazopanib	ritodrine	trimipramine
magnesium hydroxide	pegaspargase	rivaroxaban	triptorelin
magnesium oxide	peginterferon alfa-2a	rivastigmine	typhoid vaccine, live
maprotiline	peginterferon alfa-2b	romidepsin	ubrogepant
mefloquine	peginterferon beta-1a	rosuvastatin	valbenazine
mesoridazine	penicillamine	salmeterol	vandetanib
metaproterenol	penicillin g benzathine	saquinavir	vardefafil
methadone	penicillin g potassium	secnidazole	vasopressin
methicillin	penicillin g sodium	senna	vemurafenib
methotrexate	penicillin v potassium	sertraline	venlafaxine
methotrimeprazine	pentamidine	sevoflurane	vigabatrin
methylergonovine	perflutren	simvastatin	vinblastine
methysergide maleate	perphenazine	siponimod	vincristine
metoprolol	phenolphthalein	sodium iodide i-123	vincristine liposome
metronidazole	pimavanserin	sodium iodide-i-131	vinorelbine
mezlocillin	pimozide	solifenacin	vismodegib
midostaurin	piperacillin	sorafenib	voriconazole
mifepristone	pirbuterol	sotalol	warfarin
mineral oil	pitavastatin	sparfloxacin	zafirlukast
mipomersen	pitolisant	stavudine	zalcitabine
mirtazapine	polatuzumab vedotin	sulfamethoxazole	zidovudine
moxifloxacin	polyethylene glycol 3350	sunitinib	ziprasidone
mycophenolate mofetil	polyethylene glycol 3350	tacrine	
mycophenolic acid	with electrolytes	tacrolimus	
nateglinide	pomalidomide	talazoparib	
n nadolol	ponatinib	tamoxifen	
nafcillin	posaconazole	telavancin	
naldemedine	pravastatin	telbivudine	
naloxegol	primaquine	telithromycin	
naltrexone	probutol	teniposide	
nefazodone	procainamide	terbutaline	
nelarabine	procaine penicillin	terfenadine	
nelfinavir	prochlorperazine	teriflunomide	
nilotinib	promazine	tetrabenazine	
nilutamide	promethazine	thalidomide	
nitrofurantoin	propafenone	thioguanine	

